Determination of Normal Liver Stiffness by MR Elastography in Children

NCT03235414

April 18, 2019

DETERMINATION OF NORMAL LIVER STIFFNESS BY MR ELASTOGRAPHY IN CHILDREN

1. ABSTRACT:

MR elastography (MRE) is playing a growing role in the non-invasive diagnosis and monitoring of liver disease in the pediatric population. There is, however, little data specific to the use of this technique in children with existing data and techniques largely extrapolated from adult studies. Existing studies suggest that liver stiffness values may be different between children and adults [Etchell, Xanthakos]. As such there is an unmet need for uniquely pediatric data in both healthy and diseased cohorts. To address the need for such data, we plan a multi-site, prospective study of healthy pediatric (<18 years of age) volunteers to determine normal liver stiffness measured by MR elastography across the range of MRI equipment.

2. PURPOSE OF STUDY:

The primary purpose of this study is to determine normal liver stiffness values (and associated normal ranges) as measured by MR elastography for two pediatric age groups.

Secondary purposes of this study include:

- 1. To assess for cross-platform (different MRI vendors) variability in normal MRI liver stiffness values.
- 2. To assess for cross-field strength (1.5T vs. 3T) variability in normal MRI liver stiffness values.
- 3. To assess for sex-related (male vs. female) differences in normal MRI liver stiffness values.

3. BACKGROUND:

Pediatric chronic liver disease encompasses both inherited and sporadic diseases, all of which have the potential to progress to liver fibrosis and may ultimately require liver transplantation due to cirrhosis or development of hepatocellular carcinoma. Non-alcoholic fatty liver disease (NAFLD) is rapidly eclipsing other causes of liver disease in the pediatric population and is now the second most common indication for liver transplantation in the adult population [Vos].

MR elastography is becoming increasingly available, and, alongside ultrasound elastography, is playing a growing role in the non-invasive diagnosis and monitoring of liver disease. There is an increasing body of literature demonstrating the diagnostic efficacy of MR elastography in adult patients. Studies at both 1.5 and 3T have demonstrated significant positive correlation between MRI liver stiffness and pathologic grades of liver fibrosis and significant predictive accuracy for discriminating significant from little to no fibrosis in a variety of disease states [Yin, Yoshimitsu, Kim]. MR elastography currently has advantages over other tissue elastographic techniques. These advantages include the ability to evaluate the liver in its entirety, ability to characterize tissue composition in terms of fat and iron content, and standardization

across manufacturer platforms, since the vast majority elastography hardware and software currently comes from a single company (Resoundant Inc.; Rochester, MN).

While MR elastography is being used in pediatric and young adult patients and is particularly attractive in this population due to its non-invasive nature (cf biopsy), the body of literature supporting its use in this population is relatively small. To date, the only uniquely pediatric study of MR elastography that has explored diagnostic performance of the technique is a study of 35 subjects, mean age of 13 years, with suspected liver disease who underwent both MRE and liver biopsy [Xanthakos]. That study by Xanthakos et al. found that a cut-off of 2.71 kPa provided optimal sensitivity (88%) and specificity (85%) for distinguishing F0-F1 (no to little) from F2-F4 (moderate to severe) fibrosis. Of note, this cut-off is lower than the mean stiffness values previously reported for F2 fibrosis in adult studies (3.87±1.85 kPa) raising the possibility that both normal and pathologic liver stiffness may differ between pediatric and adult patients (3). Importantly, there were no subjects without liver disease in this study by Xanthakos et al. to define normal liver stiffness values.

There is one prior study of healthy pediatric patients that included 35 subjects (24 between ages 5-14 years and 11 between ages 15-18 years)[Etchell]. That study demonstrated that normal liver stiffness values were lower for healthy pediatric subjects than for healthy adult subjects (2.2 vs. 2.6 kPa). The authors also found a slight significant correlation between age and liver stiffness (r=0.38) but failed to demonstrate a difference in liver stiffness between subjects ≤14 years of age versus >14 years of age. While this prior study provides some information about normal liver stiffness in the pediatric population, it has key limitations. First, this study was performed with nonstandard multi-frequency MR elastography. One of the frequencies that was utilized (56 Hz) is close to the standard 60 Hz MR elastography utilized for clinical MRE, but differences in frequency utilized to measure tissue stiffness are known to influence liver stiffness measurements and thus normative data from this study may not apply to MR elastography performed with manufacturer standard technique. Second, the subjects imaged in this study were not fasting at the time of MR imaging. There are conflicting data regarding the effect of fasting (or lack thereof) on measured liver stiffness with some studies showing a stiffening effect of increased post-prandial splanchnic blood flow [Hines, Lemoine, Yin]. Third, while the subjects included in this study had no "known history of liver disease" MR fat fractions were not measured and serum liver function tests were not checked to confirm liver health. Finally, all examinations in this prior study were performed on a single manufacturer MR platform and at a single field strength, possibly limiting generalizability across other platforms.

MR elastography is a rapidly evolving technique and sequence improvements are constantly being developed. Additionally, new MRI techniques for assessment of diffuse liver disease are constantly being developed. At CCHMC only, additional imaging data will be acquired for exploratory aims related to these newer techniques.

4. STUDY DESIGN:

Study aims and hypotheses are as follows:

Primary aim/hypothesis – To determine normal liver stiffness values (and associated normal ranges) as measured by MR elastography for two pediatric age groups. We hypothesize that normal liver stiffness as measured by MR elastography will differ between the two pediatric age groups, increasing with increasing age.

To achieve the primary aim, MR elastography will be performed in up to 104 healthy children, somewhat evenly divided (approximately 48 each) into two age groups (7-<12years, 12-<18years). Means, standard deviations and 95% confidence intervals for normal liver stiffness will be calculated for each age group and values will be compared across groups.

Multi-site secondary aims and hypotheses are as follows:

- To assess cross-platform variability in normal MRI liver stiffness values. We hypothesize that there will be no significant difference in mean normal liver stiffness values obtained on three different vendor platforms (GE, Philips, Siemens).
- 2. To assess for cross-field strength variability in normal MRI liver stiffness values. We hypothesize that there will be no significant difference in mean normal liver stiffness values obtained at 1.5T versus 3T.
- 3. To assess for sex-related (male vs. female) differences in normal MRI liver stiffness values. We hypothesize that there will be no sex-related differences in normal liver stiffness measured by MR elastography.

To achieve secondary aim #1, subject recruitment will be stratified across sites with approximately 32 subjects in each age group being imaged on each of the different vendor platforms (GE, Philips, Siemens). To achieve secondary aim #2, subject recruitment will be stratified across 1.5T and 3T magnets with approximately 48 subjects in each age group being imaged at each of the different field strengths. To achieve secondary aim #3, approximately equal numbers of male and female subjects will be recruited in each of the two age groups.

CCHMC exploratory aims and hypotheses are as follows:

1. To determine normal corrected T1 (cT1) values for two pediatric age groups. We hypothesize that there will be no significant difference in mean cT1 values between age groups or between field strengths.

Overall research strategy:

We propose to conduct a multi-institutional study of normal liver stiffness values in pediatric subjects with no known history of liver disease. The requirement for multiple sites relates to the need to acquire normative stiffness values on each of the three major MRI vendor platforms to assess for unexpected cross-platform variability in liver stiffness. CCHMC has Philips MRI scanners (1.5 and 3T) equipped with MR elastography but does not have access to GE or Siemens MRI scanners in a research environment. Massachusetts General Hospital (MGH) has an elastography capable GE scanner (1.5T), Children's Hospital of Philadelphia (CHOP) has elastography-capable GE and Siemens scanners (3T), and Mallinckrodt Institute of Radiology (MIR) has an

elastography-capable Siemens scanner (1.5T). This human study protocol will be submitted for approval to the Institutional Review Board at CCHMC. CCHMC will serve as the lead site. CHOP, MGH and MIR may choose to submit to their IRB or to rely on the CCHMC IRB.

Power calculation relevant to SA1: Determine normal liver stiffness values (and associated normal ranges) as measured by MR elastography for three pediatric age groups: Based on the standard deviation of normal liver stiffness measurements in the study by Etchell et al. (SD=0.3 kPa) and the confidence intervals from a study of healthy adult livers by Lee et al. (95% CI ~±0.1 kPa), we calculate that a sample size of n=18 is needed in each group to achieve 2-sided 95% confidence intervals with a distance from the mean to the limits that is equal to 0.15 kPa for each group [Etchell, Lee]. This sample size also provides 80% power to detect an effect size (Cohen's d) of 0.67 between the two age groups. Given the prior study findings of a correlation between subject age and liver stiffness, we will recruit into two subject age groups (7-<12years, 12-<18 years). Based on prior published and unpublished MRI studies of "healthy volunteers" at CCHMC, we expect up to 25% of "healthy subjects" recruited for this study will have unsuspected liver disease manifest as abnormalities in liver function tests or liver fat fraction values greater than 5% by MRI proton density fat fraction (PDFF) (12). Therefore, we will increase recruitment targets by 25% over the levels required to achieve adequate statistical power. Thus, approximately 24 subjects will be recruited to each group at each field strength for a total study recruitment of n= up to 104.

MR imaging:

All imaging will be performed using multi-channel phased-array torso coil. MR elastography will be performed utilizing the manufacturer product MRE sequence (generally 2D gradient recalled echo at 1.5T and 2D spin echo echo-planar imaging at 3T) and the manufacturer standard 60 Hz frequency. For the GRE sequence, driver amplitude will be adjusted based on patient weight (no adjustment required for SE-EPI). Per standard protocol, four axial slices will be acquired through the bulk of the central liver. PDFF sequences will be performed per manufacturer recommended settings. Total imaging time will be less than 15 minutes per examination and will be accomplished with approximately six breath holds.

Sequences acquired will include:

- 1. 3-plane localizer
- 2. MR elastography (manufacturer recommended)
- 3. PDFF sequence
- 4. Axial T2-weighted single-shot fast spin-echo (anatomic sequence)

Driver amplitude will be adjusted as follows for the GRE sequence: GRE:

Patient weight	Amplitude
40-49 kg	40%
50-59 kg	50%

60-69 kg	60%
70-79 kg	70%
80-89 kg	80%
90-99 kg	90%
100+ kg	100%

Additional sequences will be acquired at CCHMC only. These will extend the total imaging time to up to 30 minutes and additional breath holds.

Corrected T1

MR exam post-processing:

All PDFF and MR elastography images will be processed both locally and centrally at a single site (CCHMC) by a single trained observer to ensure uniformity in post-processing technique. Post-processing will be performed as previously described with placement of single large regions of interest in the right hepatic lobe (12). Central MR elastography data will be post-processed using MRE Lab (Mayo Clinic, Rochester, MN) and PDFF data will be post-processed using Philips Intellispace (Philips Healthcare, Best, The Netherlands).

De-identified cT1 data acquired at CCHMC only will be sent to Perspectum Diagnostics for analysis.

5. DURATION:

18 months: 1 year for subject accrual, 6 months for analysis and write-up

6. SELECTION & RECRUITMENT OF PARTICIPANTS:

Healthy pediatric subjects without a known history of liver disease will be recruited via advertising through established hospital channels (e.g. email) and posted flyers and/or posters at each of the study sites. Based on prior studies of normal subjects at CCHMC, we anticipate no difficulty recruiting the required number of subjects for this study. For a prior study of pancreatic function in normal subjects that required MRI and placement of an intravenous catheter, 142 responses expressing interest in participating in the study were received within 4 days of study announcement.

For each age group, MRI vendor and field strength, approximately half the recruited subjects will be male and half will be female. CCHMC will recruit a total of 32 subjects (16 male, 16 female), CHOP will recruit up to 40 subjects (approximately 20 male, 20 female), and MIR and MGH will each recruit a total of 16 subjects (8 male, 8 female).

Inclusion criteria:

- 1. Age 7-less than 18 years of age
- No documented history of liver disease
- 3. English speaking*

Exclusion criteria:

1. NPO less than 4 hours

- 2. Body mass index < 10th or > 85th percentile for age
- 3. Documented history of liver disease
- 4. Pregnancy
- 5. Inability to lie still for duration of the MRI
- 6. Inability to breath hold for the duration of the 15-20 second MR elastography sequence
- 7. Standard contraindication to MRI (implanted hardware, etc.)
- 8. Requirement of sedation or general anesthesia for MRI
- 9. Abnormality of any prior measured liver function test**
- 10. Any prior liver fat fraction > 5% by MRI PDFF**

*English speaking has been included as an inclusion criterion as successful performance of an MRE examination requires following detailed and repeated breath hold instructions. This is a multicenter study and interpreter services are not uniformly available in the imaging research environment across participating institutions.

**Research results meeting this exclusion will eliminate subjects from population analysis

7. PROCESS OF OBTAINING CONSENT:

Participants will be screened in advance of enrollment by study personnel to determine baseline eligibility for participation. Once eligibility has been confirmed, written informed consent will be obtained in person at the time of the research visit.

Written informed consent will be obtained in person from parents/guardians of subjects <18 years of age. In addition to parent/guardian informed consent, assent will be obtained from all subjects ≥11. Consent or assent may be obtained by study personnel inclusive of the PI, Co-Is or clinical research coordinator(s).

8. STUDY PROCEDURES:

To confirm "healthy status" and the absence of liver disease, subjects will be weighed and measured (height and waist circumference) prior to the research MRI.

Subjects will be surveyed about liver health using a survey created with the assistance of the study hepatologist and medical records (if available) will be reviewed to exclude documented liver disease (ATTACHMENT A).

Subjects will also undergo a research venous blood draw to confirm absence of elevation of markers of liver health inclusive of: AST, ALT, GGT, alkaline phosphatase, total and direct bilirubin. This research blood draw will require 2.5 mL of venous blood and will occur prior to or following the research MRI. At CCHMC the research blood draw will occur in the Schubert Research Center by SRC nursing staff. In addition, the research MRI will include a PDFF sequence to measure liver fat fraction in all subjects to identify previously unknown fatty liver disease.

Study visit structure (single visit):

1. Intake survey and anthropomorphic measurements

- 2. MRI safety screening
- 3. Research MRI exam
- Research blood draw

Drugs, Devices, and Biologics:

MR elastography equipment consists of an active and a passive driver system. The passive driver is connected to the active driver in the equipment room by a wave-guide with a hollow plastic tube. The active driver generates low amplitude (60 Hz) vibrations which are passed via pneumatic pressure to the passive driver. The initiation and cessation of the vibrations are controlled by the MR pulse sequence programmed and embedded as part of the scanner software. All MRE pulse sequences and hardware to be used for this study are sold as product by the MR vendors or an aftermarket company (Resoundant, Inc.) and all are FDA approved.

The other MRI sequences to be utilized in this study (anatomic, PDFF) are FDA approved sequences sold as product by the MRI hardware vendors.

9. DATA ANALYSIS/METHODS:

All PDFF and MR elastography images will be processed both locally and centrally at a single site (CCHMC) by a single trained observer to ensure uniformity in post-processing technique. Post-processing will be performed as previously described with placement of single large regions of interest in the right hepatic lobe (12). Central MR elastography data will be post-processed using MRE Lab (Mayo Clinic, Rochester, MN) and PDFF data will be post-processed using Philips Intellispace (Philips Healthcare, Best, The Netherlands).

De-identified cT1 data acquired at CCHMC only will be sent to Perspectum Diagnostics for analysis.

Descriptive statistics will be utilized to describe the characteristics of each subject group (age, sex, scanner manufacturer, field strength). Normal liver stiffness for each age group will be summarized as mean ± std with range and 95% confidence interval also provided. Two sample t-test or one-way analysis of variance (ANOVA) will be used to assess for differences in liver stiffness between age groups and between different groups of categorical variables (sex, scanner manufacturer, field strength). The correlation between liver stiffness and continuous variables will be assessed by using Pearson on Spearman correlation coefficients as appropriate. Multiple linear regression models will be utilized to evaluate the association between liver stiffness and the predictor variables adjusting for all other covariates. Box plots will be generated to visually illustrate the results from the group comparisons mentioned above. All analyses will be performed using SAS version 9.4. A p-value less than 0.05 will be considered statistically significant for all inference testing.

10. FACILITIES and PERFORMANCE SITES:

Research blood draws will occur in the Schubert Research Clinic. All other study procedures will occur in the CCHMC Imaging Research Center (IRC).

11. POTENTIAL BENEFITS:

There are no direct benefits to study participants. This research, however, is critical for our understanding of normal MRE values in children which are relevant to the diagnosis of disease utilizing MRE. Therefore this research has potential future benefit to children with known or suspected liver disease.

12. POTENTIAL RISKS, DISCOMFORTS, INCONVENIENCES AND PRECAUTIONS:

There are no known risks from having an MRI or from use of the sequences being investigated for appropriately screened patients. However, some people are claustrophobic and may become anxious, fearful, or nervous in the scanner. Should participants become uncomfortable at any time the scan will be stopped immediately. Should any previously unknown risks related to having an MR examination be identified during the course of this study, that information will be relayed from individual site PIs to the lead PI at CCHMC and participants will be informed of those risks.

A board-certified radiologist will review the MRI exam. Any unexpected finding requiring further medical evaluation will be shared with the participant and/or the participant's physician. For any finding deemed not related to the study there will be no further follow-up by the study team. The research MRI exam will be identified by a number assigned as a part of the research study and will not become a part of the participant's permanent medical record.

There are no specific risks to pregnant patients from having the short MRI examination as part of this study.

Research blood draws may be associated with transient mild discomfort and the potential for mild bruising or fainting.

There is minimal risk of loss of confidentiality through study participation (see PRIVACY AND CONFIDENTIALITY BELOW).

13. RISK/BENEFIT ANALYSIS:

This study is minimal risk with no direct benefit to study participants. The primary risks relate to physical discomfort (blood draw, possibly MRI) and potential loss of confidentiality.

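### Age inside the two wide age bands is not controlled at recruitment, although the primary hypothesis is a rise in stiffness with age

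*Combined protocol and SAP*

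**What the plan says.** Section 4 (Study Design, primary aim) has the children "somewhat evenly divided (approximately 48 each) into two age groups (7-<12years, 12-<18years"). The hypothesis there is that stiffness "will differ between the two pediatric age groups, increasing with increasing age". Under the secondary aims, section 4 stratifies recruitment by vendor and field strength and asks for about equal numbers of each sex per age group. Section 6 repeats the sex balance for each combination of age group, vendor and field strength.

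The only other age rule is the eligibility range of 7 to under 18 years. Neither section gives a quota, minimum count or target distribution for age inside a band.

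Recruitment is by open advertising. Section 6 excludes children who cannot lie still, who need sedation or anaesthesia, or who meet this criterion: "Inability to breath hold for the duration of the 15-20 second MR elastography sequence". Section 8 adds a venous blood draw.

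Section 9 summarises stiffness by age group and compares groups by t-test or ANOVA. It also plans correlations with continuous variables and a multiple regression. Age is not named in either.

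**The concern.** The bands are 5 and 6 years wide. If stiffness rises with age, the expected difference between them is the slope times the gap between their mean ages. The plan fixes the head counts and leaves that gap to whoever volunteers. Every factor in the secondary aims is balanced at recruitment, while the variable in the primary hypothesis is controlled only at the cut point of 12 years.

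A skew towards the older end of the lower band is plausible, because holding the breath, lying still and accepting a blood draw may be harder for a child of 7-9 than for one of 10-11. The head count could be met with less power than planned, and a null result could reflect who volunteered. The lower band's normal range could also rest mainly on 10-11 year-olds.

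The background section shows that a two-band contrast can miss a gradient. Of the prior study in healthy children it reports: "The authors also found a slight significant correlation between age and liver stiffness (r=0.38"), and then says that no difference was shown between children up to 14 and those older.

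**Working it through.** **Inputs from the documents.** SD 0.3 kPa; Cohen's d 0.67; 25% inflation; about 24 recruited per age group at each field strength (section 4, power calculation). For alpha, section 9 says: "A p-value less than 0.05 will be considered statistically significant for all inference testing". I take the t-test as two-sided.

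**The plan's own figures.** The plan says "a sample size of n=18 is needed in each group to achieve 2-sided 95% confidence intervals". Its target half-width is 0.15 kPa. The half-width is t(0.975, n-1) × 0.3/√n: 0.149 at n = 18 and 0.154 at n = 17, so 18 reproduces. Inflation gives 18/0.75 = 24 per field strength, or 48 per age group. Power for d = 0.67 is 80.1% at 36 per age group (18 × 2 field strengths) and 49.7% at 18. The stated 80% therefore reproduces on the reading of 36 evaluable per age group, which I use below.

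**Assumptions.** The age trend is linear. It gives 0.2 kPa (d = 0.2/0.3 = 0.67) when ages are evenly spread, with mean ages 9.5 and 15.0 and a gap of 5.5 years. The slope is 0.2/5.5 = 0.0364 kPa per year. The upper band stays evenly filled (mean 15.0).

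**Skew in the lower band.** Let c be the entry rate for each year of age 7-9 relative to ages 10-11.
- Share aged 7-9 = 3c/(3c + 2).
- Mean age = [c(7.5 + 8.5 + 9.5) + 10.5 + 11.5]/(3c + 2).
- d = 0.0364 × gap/0.3, with power from the noncentral t at 36 per group.

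| c | Aged 7-9, of 36 | Lower mean age | Gap (years) | Difference (kPa) | d | Power |
|---|---|---|---|---|---|---|
| 1 | 22 | 9.50 | 5.50 | 0.200 | 0.67 | 80% |
| 0.5 | 15 | 9.93 | 5.07 | 0.184 | 0.61 | 73% |
| 0.25 | 10 | 10.32 | 4.68 | 0.170 | 0.57 | 66% |
| 0.1 | 5 | 10.67 | 4.33 | 0.157 | 0.52 | 59% |
| 0 | 0 | 11.00 | 4.00 | 0.145 | 0.48 | 53% |

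**Information on ages 7-9.** By the same half-width formula, 22 children give 0.13 kPa, 10 give 0.21 and 5 give 0.37, against the 0.15 kPa that the plan sets for a whole group.

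**Sensitivity to the slope.** Using r = 0.38 instead, slope = 0.38 × 0.3/(SD of age). The SD of age is not given; I assume 3.75 years (range 3.0-4.5). Power is 65% (49-83%) with even ages and 40% (29-56%) if the lower band is filled only from 10-<12. The pattern is the same. At 3.75 years the even case is already below 80%, so that part of the shortfall comes from the assumed effect and not from recruitment.

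**The case against.** Three stronger readings are tempting, and the documents support none of them.

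- **That the criteria screen out the youngest.** They are based on ability, ages 7-9 are eligible, and no failure rate by age is given. An uneven burden is a reasonable expectation, not a documented fact.
- **That ages 7-9 will be almost empty.** This needs an entry rate near one tenth of that at ages 10-11, and nothing in the documents points to one.
- **That power drops to 43% or 25%.** Those figures arise only if the upper band is also cut short (9-<12 with 12-<16, or 10-<12 with 12-<15). The criteria do not explain why older teenagers would be missing, so these cases are hypothetical.

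It can also be said that the primary aim is first to estimate values per age group. The precision of each group mean depends on the count and the SD, so a narrower age gap leaves it intact. Under the slope above, the lower band's mean would move by only 0.200 - 0.157 = 0.043 kPa at a one-tenth entry rate. This stands: the loss falls on the between-group test and on how far the lower range represents ages 7-9.

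Finally, section 9 already describes age per group and plans correlation and regression. A reader could therefore see a compressed gap, and age could enter as a continuous variable. That answers the point in part, but age is not named there and no analysis can supply ages that were not recruited.

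**Conclusion.** The concern holds in a limited form. Age inside the bands is uncontrolled, and the primary between-group comparison is exposed to that. With 36 evaluable per group, a linear trend giving d = 0.67 at even spread and an evenly filled upper band, power runs from 80% down to 53% as ages 7-9 go from evenly represented to absent. Partial skew gives 73%, 66% or 59%. How much skew will occur cannot be read from the documents. This is a worthwhile, inexpensive improvement; it does not show that the planned sample is inadequate or that young children will be missing.

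**What to change.** In section 4 (primary aim) and section 6, add study-level recruitment targets of about half of each age group in each sub-band: 7-<9.5, 9.5-<12, 12-<15 and 15-<18. That is about 24 to 26 children each (96/4 = 24 at 48 per group; 104/4 = 26 at the ceiling). Do not nest the targets within vendor-by-field-by-sex cells, which would become too small to fill.

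Treat 60% from one sub-band as an outer limit and not as the target. If both bands reached it on the side next to 12, the mean ages would be 0.4 × 8.25 + 0.6 × 10.75 = 9.75 and 0.6 × 13.5 + 0.4 × 16.5 = 14.70. The gap would be 4.95 years, d 0.60 and power about 71%.

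Report screening failures by age, and in section 9 name continuous age in the correlation and the regression.

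The cost is a few protocol sentences, a shared enrolment tally across sites and possibly slower filling of the youngest sub-band. No extra children or scans are needed. Section 6 says "we anticipate no difficulty recruiting the required number of subjects for this study" and cites 142 responses in 4 days to an earlier study. That suggests spare capacity but does not show the ages of those volunteers.

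### The vendor, field-strength and sex hypotheses predict no difference, but the plan has only p<0.05 difference tests and no interval, margin or power for those contrasts, so a non-significant result cannot show agreement

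*Combined protocol and SAP*

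**What the plan says.** Section 4 (Study Design) sets three multi-site secondary hypotheses:

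- Vendor: "We hypothesize that there will be no significant difference in mean normal liver stiffness values obtained on three different vendor platforms (GE, Philips, Siemens".
- Field strength: "no significant difference in mean normal liver stiffness values obtained at 1.5T versus 3T".
- Sex: "We hypothesize that there will be no sex-related differences in normal liver stiffness measured by MR elastography".

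Under the overall research strategy in the same section, the need for several sites is explained as being "to assess for unexpected cross-platform variability in liver stiffness".

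Section 9 (Data Analysis/Methods) plans a two-sample t-test or one-way ANOVA across age groups and "between different groups of categorical variables (sex, scanner manufacturer, field strength". It adds: "Multiple linear regression models will be utilized to evaluate the association between liver stiffness and the predictor variables adjusting for all other covariates". Box plots illustrate the group comparisons. The decision rule is "A p-value less than 0.05 will be considered statistically significant for all inference testing".

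The only confidence intervals promised are those attached to the age-group summaries ("Normal liver stiffness for each age group will be summarized as mean", with SD, range and 95% interval). The power calculation in Section 4 is labelled as relevant to SA1 and covers the age groups only. Section 4 also gives approximate recruitment counts by vendor, field strength and sex, but ties them to no precision, power or margin.

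**The concern.** A difference test can give evidence against equal means. Failing to reject does not give evidence for them: p≥0.05 can arise because platforms agree or because too few children were scanned, and a p-value alone does not separate the two. The documents do not say that p≥0.05 will be reported as equivalence, but they supply no other criterion for these hypotheses.

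This bears on how the normal values will be used. Section 3 criticises the earlier study of healthy children for using one manufacturer and one field strength, and the multi-site design exists to answer that. A user who wants to apply one normal range on every scanner needs to know how large a platform difference the data still allow, and the plan does not commit to reporting it.

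Section 3 also illustrates the problem. The earlier 35-subject study found a significant age correlation (r=0.38) yet no significant difference between its two age groups. The protocol relies on the correlation, not on the null group test, when it sets up two age groups.

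**Working it through.** **The plan's own figures.** With SD 0.3 kPa and n=18, the 95% half-width for a mean is t(0.975, 17)×0.3/√18 = 0.149 kPa, which matches the stated 0.15. Allowing for 25% exclusions, 18/0.75 = 24, which also matches. The stated 80% power at d=0.67 needs 36 per age group, so it reproduces (80.1%) if it refers to 18 at each of two field strengths. It concerns age only. In kPa, 0.67×0.3 = 0.20.

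**Group sizes.** Read literally, the counts in Section 4 (32 per vendor and 48 per field strength, in each age group) imply 32×3×2 = 192 and 48×2×2 = 192 subjects, against a ceiling of 104. I therefore used the site totals in Section 6 (32, 40, 16, 16) and the scanners listed in Section 4, and assumed an even split at the two sites with two scanners.

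| Factor | Recruited | With 25% excluded |
|---|---|---|
| 1.5T vs 3T | 16+16+16 = 48 vs 16+40 = 56 | 36 vs 42 |
| Male vs female | 52 vs 52 | 39 vs 39 |
| Philips / GE / Siemens | 32 / 16+20 = 36 / 16+20 = 36 | 24 / 27 / 27 |

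**Two-group tests (two-sided 0.05).** SE = SD×√(1/n₁+1/n₂). The chance of p≥0.05 comes from a noncentral t with noncentrality shift/SE. For field strength with 25% excluded, SE = 0.3×√(1/36+1/42) = 0.0681. A 0.15 kPa shift gives noncentrality 2.20 against a critical value of 1.992, so the miss probability is 0.415. The 95% half-width is 1.992×0.0681 = 0.136 kPa.

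**Three-vendor ANOVA, one vendor shifted.** λ = [n_s(N−n_s)/N]×(shift/SD)². With 25% excluded and a 0.15 kPa shift:

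- Philips shifted: λ = (24×54/78)×0.25 = 4.15, miss probability 0.585.
- GE or Siemens shifted: λ = (27×51/78)×0.25 = 4.41, miss probability 0.563.

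**Chance of p≥0.05 at SD 0.3 kPa**

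| True shift | Exclusions | Field | Sex | Vendor |
|---|---|---|---|---|
| 0.15 kPa | 25% | 0.415 | 0.413 | 0.563–0.585 |
| 0.15 kPa | none | 0.288 | 0.286 | 0.438–0.465 |
| 0.20 kPa | 25% | 0.174 | 0.172 | 0.310–0.338 |
| 0.20 kPa | none | 0.081 | 0.080 | 0.178–0.203 |

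**Sensitivity.** If regression on age removed the variance implied by r=0.38, the residual SD would be 0.3×√(1−0.38²) = 0.277. With a 0.15 kPa shift and 25% excluded, the miss probabilities become 0.347 (field) and 0.499–0.524 (vendor). At a 0.25 kPa shift with SD 0.3 and 25% excluded, they fall to about 5% (field, sex) and 12–14% (vendor). Over an assumed SD range of 0.2 to 0.4, the field-strength miss probability at 0.20 kPa with 25% excluded runs from about 1% to 42%.

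**What intervals would show.** Expected 95% half-widths for the differences are 0.136 (field), 0.135 (sex) and 0.164–0.169 kPa (vendor pair) with 25% excluded. With none excluded they are 0.117, 0.117 and about 0.141–0.146.

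**If equivalence were claimed.** This rule requires the 90% interval to lie inside the margin, and for vendor all three pairs must pass. The documents give no margin, so 0.20 and 0.25 kPa are illustrations. Results are from simulation with 400,000 runs.

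| Case | Margin 0.20 | Margin 0.25 |
|---|---|---|
| Field, true difference 0, 25% excluded | 79% | 95% |
| Vendor, true differences 0, 25% excluded | 25% | 61% |
| Vendor, true differences 0, none excluded | 49% | 83% |
| Field, true shift 0.15 kPa, 25% excluded | 18% | 42% |

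**The case against.** The aims themselves are worded as assessments, and looking for unexpected variability is a detection task that a difference test serves. For vendor and field strength the hypothesis is of no *significant* difference, so p≥0.05 is literally the predicted result, and no section promises a claim of equivalence. The regression will yield adjusted differences from which intervals follow, and box plots are planned. Field strength and sex have about 83% power at 0.20 kPa even with 25% excluded; the clear shortfall is vendor, at 66–69%. The 0.15 kPa shift is a half-width for a single mean that no section calls clinically important, the SD comes from a study using a different technique, and 25% is the protocol's upper expectation. Finally, vendor is tied to site, and pulse sequence generally differs by field strength, so even a tight interval would not isolate the scanner effect.

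Much of this is fair, and it limits the point to secondary aims and to reporting. It does not remove the defect. A hypothesis that p≥0.05 satisfies whatever the sample size tells a reader nothing about agreement. Box plots show the spread of individual values, not the uncertainty of a difference in means. The regression intervals are available, but the plan does not commit to reporting or interpreting them. The confounding with site and sequence limits what a difference can be attributed to; it is no reason to leave its size unreported.

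**Conclusion.** The concern holds. The three secondary hypotheses predict an absence of difference, and the plan contains nothing that could demonstrate one. It should be corrected, but it does not touch the primary aim. The gap is largest for vendor, the comparison given as the reason for using several sites: with 25% excluded, a 0.15 kPa shift in one vendor would more often be missed than found. For field strength and sex, detection at 0.20 kPa is reasonable and the gap is mainly one of reporting. These sizes assume SD 0.3 kPa, two-sided testing at 0.05, even scanner splits at the two-scanner sites and a single shifted vendor. They change substantially with the SD and the shift chosen. The finding that no interval, margin or power is specified for these contrasts depends on none of those assumptions.

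**What to change.** In Section 9, commit to reporting the mean difference with a 95% confidence interval for field strength, for sex and for each pair of vendors, both unadjusted and from the planned regression, together with platform-specific means. State that a non-significant p-value will not be read as absence of a difference. In Section 4, reword the three hypotheses as estimation aims, and note that vendor differences cannot be fully separated from site, nor field strength from pulse sequence.

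If the sponsor wants to claim no relevant difference, it should set and justify its own margin before analysis, require the 90% interval to lie within it (for vendor, all three pairs), and otherwise report the comparison as inconclusive.

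The cost is protocol and analysis wording, with no extra subjects. The downside is that some comparisons will be inconclusive, and a vendor equivalence claim may often fail even when the platforms are identical. Widening the margin to avoid this raises the chance of declaring agreement when a real shift exists.
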